After allocating the villages to intervention and control arms, there were 12 villages where there was a possibility of contamination because these villages were contiguous with a village in a different arm of the study. To compensate for potential loss of statistical power due to contamination we therefore selected an additional 12 villages (6 intervention and 6 control arm) for inclusion in the study as follows: Of the 53 villages remaining in the sampling frame, we excluded 24 due to their close proximity to villages which had already been selected for the study. From the remaining 29 villages in the sampling frame, an additional 12 villages (6 intervention arm and 6 control arm) with 19 high schools (9 intervention arm and 10 control arm) were randomly selected to be included in the study.

Thus a total of 80 villages (40 in each arm) with 144 high schools (71 intervention arm and 73 control arm) will be included in the study (see diagram below).

Summary diagram

Data collection

In each of the intervention and control villages, quantitative and qualitative assessments will be carried out, both at baseline and following the intervention, among the target groups listed in Table 1.

Closed-ended questionnaires (used in the sequential cohort studies among adolescent girls and their families) have been developed based on a review of available measurement tools. Questionnaires are in Appendix 2. All instruments will initially be developed in English, translated into *Kannada* (the local language), pretested and piloted and revised, and then back-translated. Tables 4, 5 and 6 provide summaries of the different major domains and sub-domains under each indicator that will be measured in these sequential cohort surveys among the adolescent girls and their parents, respectively.

Table 4: Indicator domains and sub-domains that will be measured in sequential cohort studies of SC/ST adolescent girls in control and intervention villages, using a structured behavioural questionnaire

Major domains	Minor domains
Impact and long-term outcomes	
Demographics	Geographic location, school, age, caste, age at menarche, number of siblings in the family (male and female), parents' living status, their education, occupation, land holdings and household income, whether anyone in the family is a Devadasi/sex worker, and relationship to the adolescent girl

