Demographics	Geographic location, relationship to adolescent girl, age, caste, number of children (male and female), current marital status, education, occupation, land holdings and household income, whether anyone in the family is a Devadasi/sex worker, if yes, relationship to the adolescent girl
Medium-term outcomes	
Accessibility and expanded opportunities to enter and continue formal secondary education	Respondents' perception of the availability and accessibility of secondary school education (cost, infrastructure, transport, distance, school environment, attitudes of teachers/schools) Respondents' perceptions of opportunities to secondary education (extended family support, support from the community/neighbourhood, livelihood and economic opportunities after secondary education)
Engagement and accountability for education of adolescent girls	Support and value for education, engagement with school/neighbourhood/project staff on adolescent girl education, perceived economic/social benefits/burdens of girls' education to the family Number of visits to the school, reason, number of times enquired with daughter on syllabus or performance or school activities, appreciation, allocating time Decision and barriers
Changes in gender norms around education and marriage of girls	Respondents' perception and attitude on relative education and marriage of boys and girls, Number of years a girl and a boy to be educated. Perception about age at marriage of boys and girls, How soon the girls and boys to be get married, Perception about girls roles in household chores in relation to education and in relation to boys
Short-term outcomes	
Aware of issues, schemes and option	Whether aware of girls issues; whether aware of each of the existing government schemes/subsidies to encourage education; whether aware of various options available; whether their girl is currently availing them, reasons for not availing the services
Participation in campaigns and discussions and problems solving	Whether families participate in campaign addressing girls education and marriages; do they discuss the issues; with whom they discuss and how are they solving their problem
Allowing girls to attend special/tuition classes	Whether aware of the special/tuition classes for girls at school; whether their girl is currently availing these services; reasons for not availing; discuss subject matter with girl and tuition teachers;

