'Champions' who will be identified and trained as a part of the intervention and natural leaders within the intervention community, including panchayat²⁰ members, caste based leaders etc, will be selected as participants for the study. They will be chosen in the early part of the intervention based on their influence in the general community, their interest in the issues of education of girls and early marriage, and their ability to speak on these issues. These are the individuals who will be involved in intervention strategies to create a supportive environment for dialogue and action on the education of girls and early marriage, and to improve the levels of awareness on these issues in the community.

These interviews will measure medium-term outcomes at the community level. The tool used for data collection will be a semi-structured interview guide. The leads and probes will be developed around the changes in the general community as perceived by the champions linked to the intervention activities. Intervention activities will include folk shows and street plays conducted in all intervention villages once a year incorporating issues around educating girls and the consequences of early marriage for girls, community events like rallies and campaigns conducted in association with the intervention on issues such as the rights of girls to education and the adverse effects of early marriage.

In-depth interviews with policymakers

'Policy makers' are state, district and sub district level officials of various Government departments who will be identified as part of the intervention. These officials will be selected for participation in the study during the course of the intervention based on their ability to change or influence policies at the state, district and sub-district level, on the education of girls and early marriage.

²⁰ The Panchayat is the smallest unit of government institution in India and usually serves one or two villages.

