During the start-up period, the baseline data collection instruments and protocols will be developed and finalized, and the data collection teams will be recruited and trained. The following three months will be devoted to baseline data collection. The last 9 months of the project will be devoted to end line data collection (three months), analyses and reporting (six months), and dissemination of the findings to the local communities, to Indian policymakers, and to the international community. Interim analyses will be conducted on a semi-annual basis, and a final report submitted upon completion of the project.

The diagram below shows when key study activities will take place (greyed boxes).

Year		2013		2014				2015				2016				2017				2018	
Quarter		3	4	1	2	3	4	1	2	3	4	1	2	3	4	1	2	3	4	1	2
Quantitative Studies																					
Cohort-1: Intervention & Control site																					
1	Girls																				
2	Family members of girls																				
Cohort-2: Intervention & Control site																					
1	Girls																				
2	Family members of girls																				
3	Principals, teachers and SDMC members																				
Qualitative Studies																					
1	Case studies (1st cohorts of girls from intervention and control, 2 nd and 3 rd cohort drop-outs from intervention)																				
2	IDI with girls, families, teachers, boys (intervention)																				
3	IDI- Champions																				
4	IDI- Policymakers																				
Intervention in intervention clusters																					

Ethical issues

Interviews will be conducted in private settings in a sensitive and non-judgmental manner. Since some of the participants will be minors, we will seek both written informed consent from the girl's parent or legal guardian (if she is unmarried) and informed assent of the girls. We will seek independent informed consent from girls who are married and living with their husband.

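### Community-level outcomes are assigned to interviews with leaders who help deliver the programme in intervention villages, a source that cannot separate an intervention effect from secular change or favourable reporting

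*Protocol*

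**What the plan says.** Under process level outcomes, the protocol lists seven outcomes for the communities served by the schools, among them gender norms, community support and accountability, and vigilance over child marriage and drop-out. Study question 3 asks how the intervention affected the response of schools and communities to early drop-out.

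The section on in-depth interviews with community leaders and champions says: "These interviews will measure medium-term outcomes at the community level". It fixes the following:

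- **Who:** champions "who will be identified and trained as a part of the intervention and natural leaders within the intervention community".
- **How chosen:** partly for "their interest in the issues of education of girls and early marriage, and their ability to speak on these issues".
- **Their role:** "These are the individuals who will be involved in intervention strategies to create a supportive environment for dialogue and action".
- **What they are asked:** the probes are built around "changes in the general community as perceived by the champions linked to the intervention activities".

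The general In-depth interviews section plans 20 such interviews, semi-structured and open-ended, in year one and year four.

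The Data collection section makes a broader promise: "In each of the intervention and control villages, quantitative and qualitative assessments will be carried out, both at baseline and following the intervention".

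**The concern.** Describing mechanisms through the people who work on a programme is normal qualitative practice. The difficulty is that this section gives the interviews a different task, measurement of outcomes, and sets features that prevent them from doing it. The respondents are in one arm, they help deliver what they are asked to assess, and the link to the programme is part of the question.

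The Ethical issues section says that the same communities are targeted by other government-led development work, so change unrelated to the trial is a real possibility. If a favourable account from these interviews is reported as a community outcome, it will be read as an effect of the intervention although nothing in the source supports that attribution. The Qualitative data analysis section says that the qualitative findings will be used with the quantitative ones to understand the intervention's impact, so the reading matters for the final report.

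**Working it through.** No arithmetic applies. The protocol attaches no power, error rate or effect size to the community outcomes; the number 20 rests on an assumption of thematic saturation. The check sets the sections side by side.

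1. **Are community outcomes meant to be compared between arms?** The Policy impacts section exempts policy impacts, and only those, from between-arm comparison. The seven community outcomes are not exempted.

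2. **Is such a comparison planned?** The Analysis of primary outcomes section compares intervention and control schools, girls and families on intermediate and short-term outcomes. Communities are not named.

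3. **Do the leader interviews have a control counterpart?** None is described. Both the trained champions and the natural leaders are placed in the intervention community.

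4. **Do two rounds help?** Write the change reported by intervention-village leaders between the rounds as D = E + S + R, where E is the intervention effect, S is secular change and R is any shift in reporting among people involved in delivery. Only D is seen. A positive D is compatible with E = 0 whenever S + R is positive. Equally, D can be zero or negative, so the source is not bound to favour the programme. The section also says that respondents are chosen early in the intervention, so on the text the first round may not be a clean pre-intervention measure.

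5. **What is available in both arms?** Table 4 asks girls about support from the community and peers. Table 5 asks families about "extended family support, support from the community/neighbourhood". Table 6 asks schools about community and neighbourhood support. All three sit under medium-term outcomes. In a comparison of randomised arms, S cancels in expectation. Differential reporting is not fully removed, because respondents in intervention villages know the programme, but they are not selected as its champions.

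6. **How much of the list do those items cover?** They bear mainly on community support and on accessibility and opportunity. They do not measure norms in the wider community, participation of community members or vigilance. Table 5 has norm items, but these concern the families' own views. Coverage of the seven outcomes is therefore partial.

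7. **Do the sections agree on arms?** The Data collection section promises qualitative work in both arms. The leader section places its respondents in the intervention community. In the activity diagram under Time period, the row "IDI with girls, families, teachers, boys (intervention" carries an intervention label, the champions row carries no arm label, and the case-study row names both arms. The case studies do include control areas (20 intervention girls, 10 control).

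**The case against.** The strongest reply has four parts.

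- **The interviews are open-ended and repeated.** A reader might infer that the measure must report success even if nothing changed. The protocol does not support that. Informants can report no change, resistance or worsening, and natural leaders such as panchayat members are interviewed alongside champions and are not described as trained by the programme. This stands, and it limits the point to lack of attribution and a risk of favourable reporting. It does not answer the point, because the natural leaders share the same arm and the same role in delivery.

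- **These interviews are not the only evidence.** Other in-depth interviews with girls, parents and stakeholders also examine community change, and the between-arm comparison of girls, families and schools is already planned. A reader might infer that the whole pathway analysis depends on champions; it does not. But most of those other interviews are labelled intervention-only in the diagram, and the planned comparison gives the leader interviews themselves no control counterpart.

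- **Context will be documented in both arms.** The Ethical issues section says so. The promise is general and is not tied to these interviews or to the seven community outcomes.

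- **Study question 3 is exploratory, and the outcomes are process-level.** This stands and bounds the consequence. It does not license the word measure for a one-arm account.

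The conflict over arms should not be overstated either. The Data collection sentence is introductory, some qualitative work is done in control areas, and the champions row has no label. What is needed is reconciliation. The champion interview guide cannot be judged from the text at hand, and nothing is inferred from that.

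**Conclusion.** The point holds in a limited form. The leader and champion interviews are given the task of measuring community outcomes, but they have no control counterpart and use respondents who help deliver the intervention and are selected partly for interest in its aims. They therefore cannot distinguish an intervention effect from secular change or favourable reporting.

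The size is a matter of scope, not of a number. It covers the seven process-level community outcomes, so far as they rest on this source, and the community part of study question 3. The co-primary and secondary outcomes come from the girls' cohorts in both arms and are untouched. No rate of favourable reporting can be put on these interviews: the protocol sets no rule for counting informants, and any figure would rest on an invented one.

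The conclusion assumes that the leader section means what it says about where respondents live. If control-village leaders are in fact to be interviewed, as the Data collection section could be read to imply, the lack of a comparison would ease, but the wording would still need correcting.

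**What to change.** 1. In the leader and champion section, replace the statement that the interviews measure community outcomes with one saying that they describe implementation and perceived mechanisms.
2. State that any claim of an intervention effect on community support rests on the between-arm comparison, already planned in the Analysis of primary outcomes section, of the community-support items in Tables 4, 5 and 6.
3. State which of the seven community outcomes those items address, and that the rest have no between-arm measure and will be reported descriptively.
4. Reconcile the Data collection sentence on qualitative work in both arms with the leader section and the activity diagram, and give the champions row an arm label.

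The cost is protocol wording. No new data collection is needed, and the planned 20 interviews stay as they are. New interviews with control-village leaders are not requested: the Process evaluation analysis section limits control-arm monitoring so as not to influence outcomes there, and such interviews would raise the same worry. The price is an open admission that part of the community list cannot support a causal statement.

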Survey data will be anonymised and a unique participant identification number will be used to link survey rounds. The identity of the participants and the information shared by them will not be revealed to anyone who does not work in the research study. At no time will any of the information given by individual participants be shared with anyone outside the primary research team, except for MSc students at LSTHM who may assist with data analysis. All questionnaires will be stored in locked filing cabinets in the KHPT offices in Bangalore after the data has been computerised. The computer data will be password protected and only the statisticians working as part of the research teams will be authorized to open/use the data. Unique identifying numbers will be used to identify the questionnaires; no identifying names will be entered with the computer data. Paper copies of

the data will be kept for 5 years after completion of the end of the study before being shredded. Computer data will become publicly available two years after completion of the study.

The purpose of the study will be introduced to the adolescent and his/her family before seeking appointments for the initial interviews. The interviewee will be administered an informed consent (assent in case of adolescents) form before the interview for collecting written or witnessed consent/assent. As part of the consenting/assenting procedure, participants will be assured that their participation is voluntary, and their decision to participate will not affect any benefits they receive from the school or the intervention. The consent and assent forms can be found in Appendix 5.

As this study will take place in government schools, in order to get the necessary permissions and directives for the schools in the study villages, KHPT has successfully advocated with the Department of Education at the State Level. The State Commissioner for the Department of Education has agreed to the intervention study and written to the education administrators at the district level in the two study districts, instructing them to support the study. They in turn will issue guidance and directives to all government schools in their districts to support the study, which includes directing that all teachers in the intervention schools attend training as part of the intervention. These government directives will help overcome the effects of any change in school administration during the course of the intervention. The co-operation of the school administration, staff and the SDMC is also being sought during the planning phase of the intervention..

For the case studies, at the end of the each session the interviewer will summarise the events lifeline with the help of the girl. In the next set of interviews the previous lifelines could be looked at the end of the session.

The study has excluded certain schools considering various technical and logistical aspects. The private and unaided schools were excluded from the study in order to ensure maximum reach to the intended communities, given the project resource constraints, and because they may not be amenable to external interventions. For the same reason urban and residential schools and schools with less than 10 SC/ST adolescent girls were also excluded. In order to ensure equity to all schools enrolled in the trial, we are applying for funding to enable the school based interventions be provided in these schools at the end of the intervention period.

As described above, the intervention is being carefully designed in order to ensure that it does not cause any unintended harm and that the changes in the community and the schools are sustained beyond the intervention period. The design has been finalized after many rounds of discussions with stakeholders at different levels. The design has attempted to take into consideration the existing structures, the regulatory environment and the cultural practices, and after ensuring buy-in of the major stakeholders, including the government.

We consider that the current intervention evaluation merits using an RCT to effectively test the impact of the intervention as the intervention is novel and untested and we therefore do not know if it will be successful or not. The intervention attempts to address the structural drivers of HIV in the presence of multiple contextual factors and we feel there is sufficient equipoise about the impact to warrant an RCT design.

The target population of the intervention are the most marginalised communities in India, who are also the target population of other government led developmental work. We plan to document the effect of the intervention and the contextual changes in both arms to carefully look at the impacts.

Data entry and analysis

The quantitative survey data will be double entered and cleaned using CPro.

Assessing baseline balance

Cluster randomized trials need to balance the design by having identical treatment group means for all variables to be included in the analysis. We expect that the trial will be largely balanced for the reasons that follow, and that any deviation from the balanced design will be assessed during the analysis stage. First, by virtue of its design, the trial has a relatively large number of clusters and individual respondents, which will likely help balance covariates across groups. Secondly, the design also accounted for the geographical unit where the school is located when randomizing the clusters in the trial. Third, as government schools, the schools included in the design are more or less of similar character. Although measures were taken to minimize imbalance, any remaining imbalances at baseline will be addressed as described below.

We will consider two criteria, first is the criterion of the variance of the treatment effect and the second is a criterion of assessing change in treatment effect as defined as the difference between the crude and adjusted treatment effect. We plan to analyze both the variance of the estimated treatment effect and the extent to which the estimated treatment effect changes by adjusting for covariates (Raab and Butcher, 2001)²¹. The approach that will be used in this trial is to assess the extent to which the adjustment of covariates will affect the estimated treatment effect. If the allocation of treatments to units is imbalanced, it is likely to produce a substantial difference between the unadjusted and adjusted estimates of the treatment effect. Using the following general expressions, which Raab and Butcher (2001) developed, this will be overcome as follows.

The estimate of the treatment effect, without any adjustment for covariates, becomes a difference in weighted cluster means of the outcome as;

$$Y_{..2} - Y_{..1} = \frac{\sum_{j:t=2} w_j y_{.j}}{\sum_{j:t=2} w_j} - \frac{\sum_{j:t=1} w_j y_{.j}}{\sum_{j:t=1} w_j}$$

where the weights are $w_j = s^2 m_j / (s^2 + t^2 m_j)$ and s^2 and t^2 are the estimates of between- and within-cluster variances as noted respectively τ^2 and σ^2 , m_j be the number of members in the j th cluster, y_{ij} be the outcome of i th member of the j th cluster and t be the different trial arms (intervention or control) as denoted by 1 or 2.

The variance of the estimated treatment effect can be estimated by

$$s^2 [1/(\sum_{j:t=1} w_j) + 1/(\sum_{j:t=2} w_j)]$$

²¹ Gillian M. Raab, Izzy Butcher (2001), Balance in cluster randomized trials, *Statistics In Medicine*, Statist. Med. 2001; 20:351{365

The study will be estimating the change in treatment effect, when adjusted for the covariates using

$$\sum_{K=1,2,\dots,p} \beta_k (x_{k,2} - x_{k,1})$$

Where β_k is the estimate of regression coefficient for predicting y from the k^{th} covariate and $x_{k,t}$ is the weighted mean of the cluster means for treatment t for the k^{th} covariate, with weights w_j as defined above and p the number of covariates.

Analysis of primary outcomes

At project completion, we will assess whether, at follow up, there are significant differences between the intervention and control girls in the key indicators of entering 8th standard, completing tenth standard, being married, having sexual debut and entering into sex work. In the course of the analysis we will present simple cluster summaries for the primary outcomes. We will perform statistical tests, using the t-statistic, to assess the significance of and differences observed between the arms.

The final analysis will assess whether the intervention and control schools, adolescent girls and their families significantly differ in terms of the intermediate and short-term outcomes. As recommended by Hayes and Moulton²², given the large number of clusters and because of reasons related to statistical efficiency, individual-level regression methods will be used to test for significant differences in outcomes between intervention and control arms. For each outcome of interest (e.g., the proportion of girls married at the end of the study period, the proportion of girls passing to 10th Standard, etc.), multivariable logistic regression models using generalized estimating equations (GEE)^{23,24} to address clustering at the school level will be estimated. Stata 11 will be used for all analyses. Similar methods will be used to compare short- and medium-term outcomes among SC/ST girls and their families between intervention and control arms.

Qualitative data analysis

The qualitative data will be transcribed and translated into English. Qualitative analysis packages (eg., NVivo9, ATLAS TI) will be used to identify key issues and themes emerging over time. These findings will be used along with the quantitative findings to understand the impact of the intervention.

Addressing confounding factors, selection bias, spill over effect and impact heterogeneity

The RCT design will reduce problems associated with confounding factors and selection bias, and there is sufficient geographic dispersion of the villages (Figure 1) to minimize spill-over effects. Further, the large sample size will help reduce the risk of missing a true effect. The comparability of the intervention and control samples will be assessed at baseline, and any differences controlled for in the final analysis. Impact heterogeneity will be addressed by examining the intensity of exposure to the intervention among the adolescent girls, their families, boys in the neighbourhood, and the associations between intensity of exposure and the outcomes of interest.

²² Hayes RJ, Moulton LH. Cluster Randomized Trials. Boca Raton: Chapman & Hall; 2009.

²³ Liang KY, Zeger SL. Longitudinal analysis using generalized linear models. *Biometrika* 1986;73:12-22.

²⁴ Zeger SL, Liang KY. Longitudinal data analysis for discrete and continuous outcomes. *Biometrika* 1986;42:121-30

Potential biases (selection, interviewer and recall biases) will be assessed and addressed in the trial as follows:

Selection bias will be largely addressed as a result of the careful process of randomization and selection of subjects. There are chances of selective loss to follow-up which can lead to a bias in the cohort. This is planned to be addressed with negative case analyses to look into reasons for dropout and triangulation of qualitative and quantitative data. The self-selection bias with those adolescent girls and families likely to drop out or refusing to participate is planned to be countered by the trust created by a careful informed consent process.

Interviewer biases will be addressed to a large extent by rigorous training of the research investigators. The training will include both class room sessions and field practices and will help ensure uniform understanding among all the interviewers and limit variations between interviewers as far as their understanding of questions, questioning and recording of questions and responses are concerned. Further, the interviewers will be masked of the study arms to avoid any biases. Biases might also occur on responses of sensitive indicators of sexual behaviours and experiences of harassments/violence, which largely will be addressed by introducing a self-complete questionnaire, linked to the rest of the questionnaire by a serial number, where the respondent will answer the questions using a pen and drop the completed questionnaire into a sealed box. This method has proven effective when administering sensitive questions on sexual behaviours, violence etc. in previous KHPT studies.

Recall biases are expected in some questions in the survey related to age of menarche, frequency of home visits, parents meetings etc and these will be adjusted after piloting. Recall biases will be addressed by the careful design of questionnaires, building a very good rapport with the respondents and motivating the respondents to correctly recall the responses, which plays critical roles and are under the control of investigators. The training would address these aspects to minimize recall biases, if any. The recall issues in case studies are addressed as the lifelines will be used as cues to recall events. Further, the monitoring system under the intervention would be collecting critical services provided as well outputs and key outcomes, which will be used to verify any recall biases that might exist.

The other biases, which might occur, will be as a result of transfers of girls from out of the study arms in which they are enrolled. The possible transfers includes, transfer of a girl from an intervention to a control and vice-versa and transfer from study arms to other schools out of study arm area, within or outside district. In the second scenario of transfers from study arm (intervention/control) to a school outside the trial, the monitoring system under the intervention will track the movement and will retain them in their respective study arms. It may be mentioned here that we do not expect such transfers of girls, particularly from an intervention to control or vice-versa as the schools in both these arms are government schools and characteristics remains more or less same.

Process evaluation analysis

The monitoring system will include individual tracking of adolescent girls and their families with unique identifiers by schools as part of the intervention. Along with recording all the services provided to each participant, it will also monitor school attendance, drop out, marriage, academic

scores etc, as well as mobility of each participant either as a result of migration, marriage, sex work etc.

While the monitoring system will track all the participants in the intervention arms on specific input, output and certain outcome indicators, in the control arms, the monitoring system will be limited to tracking only a few outcome indicators (e.g. school drop-out; marriage). This decision was taken so as not to influence the outcomes in the control arm through the effect of direct observation and data collection.

In the intervention arm, the monitoring data will be analysed and used to understand school attendance, drop-out rates, the proportion of girls marrying and the quality of education (academic scores), which again will be compared with the cohort survey data to triangulate the outcomes of interest. There will be a unique identifier in the monitoring system to flag all the survey participants so that the monitoring data pertaining to survey participants are compared with the survey findings.

In the control arm, we will be visiting each cohort member every 6 months, with the particular aim to validate their availability in the villages, so as to minimise the loss to follow up in the endline survey. The girls might have migrated as a result of family migration, marriage etc and information regarding the location of migration will be recorded and kept so that the interviewers can go to their new location to administer the questionnaire at the endline survey.

